6.1 Visit Windows

Subjects who withdraw from the study will have their data collected at the premature withdrawal (PW) visit assigned to the closest scheduled visit (either prior or post PW) where the data was scheduled to have been collected based on the protocol schedule of events. The data collected closest in time and date to protocol scheduled timing will be used for analysis.

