2.1 Schedule of Assessments

Study Phase	Treatment Period			End-of-Study or Premature Withdrawal ¹⁰
	Baseline ⁶	3-Month Visits ⁸	6-Month Visits	
Study Days (± visit window)	Day 1 (Week 28 of Study HZNP-ACT-302)	90 (± 7) Days after Last Visit	Every 180 (± 14) Days	
Informed consent/assent	X			
Medical history ¹	X			
Review of inclusion/exclusion criteria	X			
Dispense study drug ²	X	X ⁹	X	
Drug compliance ³		X ⁹	X	X
TEAE, SAE assessment ⁴	X ⁷	X	X	X
Brief physical examination	X ⁷		X	X
Vital Signs: blood pressure, pulse, temperature	X		X	X
Clinical laboratory evaluation (hematology, chemistry, urinalysis)	X		X	X
Electrocardiograms				X ¹¹
Urine pregnancy test ⁵	X		X	X
FARS				X ¹¹
Prior/concomitant medications	X ⁷	X	X	X

SAE=serious adverse event, TEAE=treatment-emergent adverse event.

¹ Changes in medical history from the Baseline of HZNP-ACT-301 will be recorded on the electronic case report forms. The medical history from the HZNP-ACT-301 study will be available for reference.

² Subjects will be given a 3-month supply of study drug at each clinic visit and an additional 3-month supply will be directly shipped to the subjects' home in between the required 6-month clinic visits. If direct shipments are not feasible, subjects will return to the clinic every three months to obtain study drug; however, assessments (other than adverse event queries) will only be performed every six months.

³ Subjects will be instructed to return all used and unused study drug vials at each clinic visit.

⁴ Adverse events occurring or worsening on or after the date of administration of the first dose of study drug through the end of the study will be considered treatment-emergent adverse events (TEAEs). All serious adverse events (SAEs) that occur on or after the date of administration of the first dose of study drug through two weeks after study discontinuation will be considered treatment-emergent SAEs (TESAEs) and will be recorded and reported to Horizon drug safety.

⁵ Only for female subjects of childbearing potential.

⁶ The Day 1 Visit of this study (HZNP-ACT-303) occurs on the same day as the EOS Visit (Week 28 Follow-Up Visit) for HZNP-ACT-302.

⁷ Findings will be recorded for both the Day 1 (Baseline) Visit of this study and the Week 28 Follow-up Visit for HZNP-ACT-302.

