8.5.2.3 Vital Signs

Vital signs (resting systolic and diastolic blood pressure in the non-dominant arm, pulse, and temperature) will be assessed at Baseline/Day 1, each subsequent 6-month assessment clinic visit, and the EOS (or PW) Visit. Blood pressure and pulse measurements will be obtained with the subject's arm unconstrained by clothing or other material and while the subject is sitting up. When possible, the same arm will be used for measurements in all study visits. Temperature will be obtained orally or via the ear.

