8.5.2.5 Clinical Laboratory Tests

Samples of blood (4.5 mL) and urine are scheduled for collection at Baseline/Day 1, each 6-month assessment clinic visit, and the EOS (or PW) Visit. Additional follow-up samples for clinical laboratory testing should be obtained as clinically indicated.

All clinical laboratory testing, with the exception of on-site urine pregnancy tests during the treatment period for females of childbearing potential, will be performed by the central clinical safety laboratory (URMC).

The following clinical laboratory tests will be performed:

- Complete blood count
- Chemistry panel
- Urinalysis

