6.3 Derived and Computed Variables

The following derived and computed variables have been initially identified as important for the analyses of Safety and Efficacy endpoints. It is expected that additional variables may be required. The SAP will not be amended for additional variables that are not related to the primary target or key secondary target variables. Any additional derived or computed variables will be identified and documented in the SAS programs that create the analysis files. If the SAP is not amended, further derivations related to primary and secondary target variables will be described in the CSR.

- 303 Baseline = The last non-missing measurement/assessment on the date of Week 26
 Visit from HZNP-ACT-302. If this measurement is missing or otherwise unavailable, it
 will be the last non-missing measurement/assessment on or prior to first dose in HZNP ACT-303.
- Study Day = Assessment Date Date of Enrollment + 1
- Change from Baseline = Value at Post-Baseline Value at Baseline
- Concomitant Medication is defined as any medication a subject has received concurrently with study treatment.
- Prior Medication is defined as any medication or therapies initiated prior to date of first dose of study drug. Medications that are started prior to the date of first dose of study drug and continue after the first dose of drug are considered to be both prior and concomitant medications.
- Treatment-Emergent Adverse Event (TEAE) A TEAE is any adverse change from the subject's baseline condition that occurs on or after the date of the first dose of study drug through the duration of the clinical study.
- Related TEAE Any TEAE with a reported relationship to study drug of 'possibly related'.
- Compliance = Calculated as the percentage of the number of vials used divided by the expected number of vials used, where the number of vials used is the number of used vials returned.

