9.2 Clinical Laboratory Evaluations

Descriptive summaries of actual (absolute) values and changes from baseline will be presented for Chemistry, Urinalysis, and Complete Blood Count. These tables will be grouped by visit, and overall treatment.

The number and proportion of subjects with clinical laboratory values below, within, or above normal ranges, at each study visit will be tabulated (shift tables) for each clinical laboratory analyte by treatment group. Normal ranges will be provided by the central laboratory (Eurofins Central Laboratory) used in this study.

Laboratory values will be displayed in data listings and those that are outside the normal range will be flagged, along with the corresponding normal ranges.

Protocol: HZNP-ACT-303 Page 15 of 19

Final Version 1.0

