9.3 Vital Signs

Descriptive summaries of actual (absolute) values and changes from baseline will be presented for all vital signs (temperature, systolic blood pressure, diastolic blood pressure, heart rate), weight, height, and BSA will be presented by visit and overall treatment. These data will be presented in a data listing by subject.

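### SAP 6.1 reassigns premature-withdrawal labs and vital signs to the closest scheduled visit, so sets from the first half of a later 6-month interval normally drop out of the by-visit tables

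*SAP*

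**What the plan says.** SAP 6.1 sets the rule for PW data: "Subjects who withdraw from the study will have their data collected at the premature withdrawal (PW) visit assigned to the closest scheduled visit". The target may be before or after the PW visit, but must be one at which the protocol schedule calls for that type of data. Where records compete, "The data collected closest in time and date to protocol scheduled timing will be used for analysis".

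The possible targets are few. Protocol 2.1 spaces the 6-month visits as "Every 180 (± 14) Days". Under Protocol 8.5.2.5, lab samples are "scheduled for collection at Baseline/Day 1, each 6-month assessment clinic visit, and the EOS (or PW) Visit". Under Protocol 8.5.2.3, vital signs "will be assessed at Baseline/Day 1, each subsequent 6-month assessment clinic visit, and the EOS (or PW) Visit". Neither is taken at the 3-month contacts.

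Reporting is by visit. SAP 9.2 says of the lab summaries: "These tables will be grouped by visit, and overall treatment". SAP 9.3 says vital signs "will be presented by visit and overall treatment". Protocol 8.6.2 and SAP 2.2.1 promise lab shift tables from Baseline to every post-dose visit.

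SAP 6.3 takes the 303 Baseline from Week 26 of HZNP-ACT-302 and, failing that, from the "last non-missing measurement/assessment on or prior to first dose" in this study.

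**The concern.** A subject who attends a 6-month visit and withdraws in the following three months has a PW set that is closest to the visit already attended. That visit has its own record, usually nearer its target day, so the PW set is not used. What decides this is where in the calendar the withdrawal fell, not the quality of the data.

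Long-term safety is the only objective (Protocol 7.1, SAP 2.1.1), and SAP 8 drops all efficacy analysis. Adverse event is one of the withdrawal categories in Protocol 8.3.3. The appended labeling describes neutropenia, thrombocytopenia and transaminase elevations, which the lab tables should be able to show. The last post-dose values of subjects who leave are part of that evidence.

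PW sets from the second half of an interval are kept, but under a 6-month label. Footnote 10 of the schedule allows them up to two weeks after drug is stopped, and the SAP text provides no off-drug flag.

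**Working it through.** The plan gives no figure on this point to reproduce. The check applies the SAP 6.1 rule to the protocol schedule.

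**Inputs from the documents:** 180-day spacing and a ±14-day window (Protocol 2.1); collection visits (Protocol 8.5.2.3 and 8.5.2.5); the two-step rule (SAP 6.1).

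**Assumptions, not in the documents:** the attended visit is uniform within its window; the PW day is uniform from that visit to the next target; no visit is missed.

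**Set-up for a later interval.** Let day 0 be the last 6-month target and day 180 the next, with midpoint day 90. The attended visit falls on day u and the PW visit on day s. The PW set is lost from the tables if s < 90 and |s| > |u|.

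**Share of all PW sets lost, by visit offset:**
- On target (u = 0): 90/180 = 50%.
- Late (u > 0): (90 − u)/(180 − u). At u = 14, 76/166 = 45.8%.
- Early (v = |u|): (90 − v)/(180 + v). At v = 14, 76/194 = 39.2%.

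**Average over the window:**
- Late: 1 − (90/14) ln(180/166) = 0.479.
- Early: (270/14) ln(194/180) − 1 = 0.445.
- Mean: 0.462. A simulation also gives 0.462, or 0.463 if PW may run to the next attended visit.

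**Share of first-half PW sets lost.** With a late or on-target visit, all are lost. With an early visit the share is (90 − v)/(90 + v), which averages (180/14) ln(104/90) − 1 = 0.859. The mean is 0.929. A separate day-by-day count, which weights every visit-day and PW-day pair equally and sets ties apart, drops 2,371 of 2,581 pairs (91.9%). In 7.6% the PW set displaces the scheduled one, so one set is still lost. Any PW visit more than 14 days past the target day loses to an in-window visit.

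**Sensitivity:**
- PW half as likely per day in the first half as in the second: 30.8%. Twice as likely: 61.7%.
- Preceding visit missed with probability m, in which case the PW set is kept: (1 − m) × 0.462. This gives 41.6%, 37.0% and 32.3% for m = 0.1, 0.2 and 0.3.

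**First interval.** Read literally, SAP 6.1 sends a PW set taken before about Day 90 to Baseline, where it is lost: 90/180 = 50%, or 33% to 67% under the same weights. SAP 6.3 does not allow a value after first dose to be the 303 Baseline, and Protocol 8.6.2 and SAP 2.2.1 promise post-dose summaries. If early PW sets are mapped to Month 6 instead, the loss is 0%. The documents do not say which applies.

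**The case against.** - **The schedule has its own EOS/PW column, marked for labs and vital signs.** If that column is a valid target, nothing need be lost; if it is not, ECGs have no target either. The wording could be clearer. But a target described as prior to or after PW cannot be the PW visit itself, and on the other reading SAP 6.1 would do nothing for labs and vital signs. ECGs are taken only at EOS/PW (Protocol 8.5.2.6), so no competing record in this study can displace them.
- **The list of planned tables is not in the text available for review, and a shell might carry a PW row.** That cannot be excluded. But SAP 12 describes the shells as supporting the SAP, and a shell should not override the assignment rule in 6.1.
- **The percentages apply to an unknown, possibly small, number of withdrawals.** This stands. They describe how the rule behaves under assumed timing, not a forecast for this trial. The first-interval range is wide because the documents conflict.
- **The harm is limited in a descriptive study.** This also stands. SAP 6.2 lists all data, and SAP 9.2 flags out-of-range labs. Clinically significant lab abnormalities count as TEAEs (Protocol 8.5.2.1.1) and are tabulated (SAP 9.1), and TEAEs leading to withdrawal have their own table (SAP 9). Exposure is listed by subject (SAP 9.6). None of this replaces the promised shift tables.

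**Conclusion.** The concern holds and should be fixed, though it does not threaten the study. In any interval after Month 6, a PW lab and vital-sign set from the first half is normally absent from the by-visit summaries and, for labs, the shift tables. It survives only if the earlier visit was missed or lay further from its target day.

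Under uniform timing with no missed visits, the loss is about 46% of all PW sets in later intervals. It ranges from 31% to 62% under unequal timing, and is 32% to 42% with 30% to 10% of preceding visits missed. In the first interval it is anywhere from nothing to about half under uniform timing, depending on how SAP 6.1 and 6.3 are reconciled. The direction follows from the text; the sizes rest on assumed timing. ECGs and listings are unaffected.

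**What to change.** In SAP 6.1:
- Make PW its own post-baseline analysis visit, with its own row in the by-visit lab and vital-sign tables and in the lab shift tables.
- Keep that row separate from EOS, because completers are assessed while still on drug.
- State that no record after first dose is assigned to Baseline, in line with SAP 6.3.
- Flag PW values taken after the last dose.

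The cost is a few sentences and one extra row in existing tables, with no new data. There are two drawbacks: the PW row pools values from different times on study, and the next 6-month row loses the PW values now carried forward to it.

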6.2 Data Adjustments, Handling, Conventions

All collected data will be presented in listings. Data not subject to analyses according to this plan will not appear in any tables or graphics but will be included only in the data listings.

Adverse events will be coded using the Medical Dictionary for Regulatory Activities (MedDRA) (version 16.1). Concomitant medications will be coded using World Health Organization Drug Dictionary (WHO-DD) (version March 1, 2013).

If partial dates occur, the convention for replacing missing dates for the purposes of calculating derived variables is as follows:

For partial start dates:

- If the year is unknown, then do not impute the date but assign a missing value.
- If the month is unknown, then:
 - o If the year matches the year of enrollment date, then impute the month and day of the randomization date.
 - o Otherwise, assign 01 January
- If the day is unknown, then:
 - o If the month and year match the month and year of the enrollment date, then impute the day of the first dose date.
 - o Otherwise, assign 01

For partial end dates:

- If the year is unknown, then do not impute the date but assign a missing value.
- If the month is unknown, then assign the last day of the year, 31 December.

If the day is unknown, then assign the last day of the month.

If an AE has a missing severity, it will be imputed as 'Severe'; any missing relationship to study drug of an AE will be imputed as 'Related'. No other missing data will be imputed unless otherwise specified.

In general, for quantitative laboratory values reported as '<' or '≤', the lower limit of quantitation (LLOQ), or limit of detection (LOD), the reported value (i.e., LLOQ, LOD) will be used for analysis).

For quantitative laboratory values reported as '>' or '\geq', the upper limit of quantitation (ULOQ), the reported value (i.e., ULOQ) will be used for analysis.

For analysis purposes, repeat laboratory test results will not be used unless the original laboratory value is missing or indicated as invalid, in which case the first non-missing repeat

Protocol: HZNP-ACT-303 Page 12 of 19

Final Version 1.0

laboratory value will be used for data analysis.

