8.5.4.1 Baseline/Day 1 (Week 28 of Study HZNP-ACT-302)

The Baseline/Day 1 Visit of this study (HZNP-ACT-303) occurs on the same day as the EOS Visit (Week 28 Follow-Up Visit) for HZNP-ACT-302. At the Baseline Visit, study drug will be

distributed for administration at home according to the planned TIW dosing schedule. Clinic staff will perform the following procedures:

- Obtain signed, written Informed Consent/Assent and permission to use Protected Health Information (in accordance with the Health Insurance Portability and Accountability Act [HIPAA]) for Study HZNP-ACT-303. Refusal to provide this permission excludes an individual from eligibility for study participation. Record date Informed Consent/Assent was given and who conducted the process on the appropriate source documentation.
- Perform review of inclusion/exclusion criteria.
- Record any changes in medical history since Baseline of HZNP-ACT-301.
- Perform brief physical examination¹, including vital signs.
- Enquire about adverse events¹ and concomitant medications¹.
- Collect blood (4.5 mL) and urine samples for safety clinical laboratory values (including urine pregnancy test [if applicable]).
- Dispense a 3-month supply of study drug.

¹ Findings will be recorded for Day 1 (Baseline) of this study and for the EOS Visit (Week 28) of previous study (HZNP-ACT-302).

Subjects will be discharged from the study center after all of the Study Day 1 procedures have been completed. Subjects who are able to receive study drug shipped directly to their home will be instructed to return to the clinic in six months, and those who are not able to receive study drug shipments at home will be instructed to return in three months.

8.5.4.2 3-Month Visits

Subjects who are able to receive direct-to-home shipments of study drug will be contacted by phone three months after the Baseline and 6-month assessment visits and queried regarding adverse events and concomitant medication use.

Subjects who are not able to receive study drug shipments at their home will return to the clinic for interim clinic visits three months after the Baseline and 6-month assessment visits, and clinic staff will perform the following assessments:

- Collect all used, partially used, and unused study medication kits and vials from the previous clinic visit.
- Enquire about adverse events and concomitant medication use
- Dispense a 3-month supply of study drug.

8.5.4.3 6-Month Assessment Clinic Visits

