9.1 Adverse Events

Missing and partially missing AE start and/or stop dates will be imputed for the purpose of statistical analysis, according to the specifications described in Section 6.2.

A summary of overall TEAEs, TEAEs, SAEs, TEAEs leading to PW, TEAEs by relationship to study drug, and severity of TEAEs will be presented by overall treatment.

Summaries and incidence rates (frequencies and percentages) of individual TEAEs by MedDRA System Organ Class (SOC) and preferred term will be displayed by overall treatment received. Such summaries will be displayed for TEAEs, SAEs, TEAEs leading to early termination, TEAEs by relationship to study drug, and TEAEs by severity

Each subject will be counted only once within each preferred term. If a subject experiences more than one TEAE within a preferred term only the TEAE with the strongest relationship or the maximum intensity, as appropriate, will be included in the summaries of relationship and intensity. No inferential statistical tests will be performed.

In the AE data listings, all AEs will be displayed.

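### SAP 6.2 matches unknown-day onsets to the enrollment month, but TEAE status depends on first dose, so a few partially dated events can be misclassified in either direction

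*SAP*

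**What the plan says.** SAP 6.3 makes an adverse change treatment-emergent if it "occurs on or after the date of the first dose of study drug through the duration of the clinical study". The reference date is therefore first dose.

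SAP 6.2 supplies the start-date imputation. For an unknown day: "If the month and year match the month and year of the enrollment date, then impute the day of the first dose date". Otherwise the day becomes 01. For an unknown year: "If the year is unknown, then do not impute the date but assign a missing value". No start-date rule looks at the stop date.

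The same section fills a missing severity and a missing relationship with the worst category, then adds: "No other missing data will be imputed unless otherwise specified".

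SAP 9.1 says "Missing and partially missing AE start and/or stop dates will be imputed for the purpose of statistical analysis", and the sentence goes on to refer to Section 6.2 for how this is done.

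Protocol 8.5.4.1 says that at the Baseline Visit drug is "distributed for administration at home according to the planned TIW dosing schedule". SAP 5 defines the Safety Population by a dose after the Baseline Visit; Protocol 8.6.3 allows a dose on or after it. Neither document gives the interval from enrollment to first dose.

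**The concern.** The unknown-day rule uses two reference dates: it tests the enrollment month but inserts the first-dose day. This is harmless while both dates lie in one calendar month. When they do not, an event in the first-dose month fails the test, receives day 01, and can be placed before first dose although it probably began on drug.

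The unknown-year rule leaves no date to compare, and nothing says how such an event is classified. Severity and relationship have a conservative default; onset, which decides entry to the TEAE tables, has none.

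Efficacy analysis has been removed (SAP 2.2, 8 and 10), so safety is all that this study reports. TEAE status governs the tables of incidence, severity, relationship and events leading to withdrawal. Events are collected by recall at contacts about three months apart, some by telephone, so unknown days are foreseeable.

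**Working it through.** The plan states no figure on this point, so there is none to reproduce. The check applies the rules as written.

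**Inputs.** The day rule and its fallback to 01 are from SAP 6.2, and the TEAE test (imputed onset on or after first dose) is from SAP 6.3. Enrollment is taken as Day 1. The lag L from enrollment to first dose is an assumption. The example schedules in Protocol 8.4.7.3 leave at most three days between dosing days, so 1 to 3 days is reasonable if the subject starts on the next dosing day.

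**Worked case.** Enrolled 29 June, first dose 2 July, event in July, day unknown.
- July does not match the enrollment month, so the SAP imputes 1 July.
- 1 July is before 2 July, so the event is not a TEAE.
- Yet 30 of the 31 possible onset days (2 to 31 July) are on drug: 30/31 = 97%.
- Matching on the first-dose month instead gives 2 July, a TEAE.

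If first dose were 1 July, the imputed 1 July would equal first dose and the event would be a TEAE. A crossing onto the 1st is harmless.

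**How many enrollment dates are exposed.** At lag L, exposure requires first dose on day 2 to L of the next month, which is L − 1 enrollment dates per month. Over 730 consecutive enrollment dates (24 month-ends), the exposed share is 24 × (L − 1)/730. Running the rule date by date gave the same counts:

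| Assumed lag (days) | Exposed dates | Share | Matching on first-dose month |
|---|---|---|---|
| 0 | 0 | 0% | 0% |
| 1 | 0 | 0% | 0% |
| 2 | 24/730 | 3.3% | 0% |
| 3 | 48/730 | 6.6% | 0% |
| 7 | 144/730 | 19.7% | 0% |
| 14 | 312/730 | 42.7% | 0% |

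These are shares of enrollment dates, not of events. A loss also needs an event in the first-dose month whose day is unknown.

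**Unknown year.** Section 6.2 leaves the date missing, offers no fallback, and 6.3 compares dates. No step assigns a status. A program that simply tests onset on or after first dose would not flag the event.

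**Stop date.** With illustrative dates: enrolled on the 10th, first dose on the 12th, event in the same month with day unknown, known stop on the 11th. The month matches enrollment, so the start becomes the 12th, after the event's own end, and a pre-treatment event is counted as a TEAE.

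**The case against.** The strongest reply is that the practical effect is small. Protocol 9 requires start and stop dates in source documents, Protocol 12 has omissions queried, and contacts are about three months apart, so an unknown year should be very rare. Events ongoing from HZNP-ACT-302 are treated as baseline signs (Protocol 8.5.2.1.2). The lag is unstated, and at 0 or 1 day the day rule loses nothing. When enrollment and first dose share a month, the rule makes every unknown-day event of that month a TEAE, which is conservative. All events are listed, the SAE and death summaries are not expressly limited to TEAEs, and the study is single-arm and descriptive. All of this stands and limits the size; none of it makes the rule correct.

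Four stronger readings are tempting but unsupported:
- A reader might infer that SAP 9.1 contradicts 6.2 by promising to impute missing dates. It does not: the sentence defers to 6.2.
- A reader might infer that every event with an unknown year is excluded. The SAP orders no exclusion; it leaves the status undefined, and exclusion is one literal programming outcome.
- A reader might take the chance of crossing a month-end (24L/730, or 3.3%, 6.6% and 9.9% at 1, 2 and 3 days) as the exposed share. That includes the harmless crossings onto the 1st.
- A reader might infer that the rules only ever remove events. The missing stop-date check adds them.

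**Conclusion.** The point holds as a flaw in a stated rule, with a small expected effect. The unknown-day rule is anchored to a different date from the TEAE definition and gives a wrong classification when first dose falls in the month after enrollment and not on the 1st. Exposure is about 0% to 6.6% of enrollment dates at assumed lags of 1 to 3 days, and higher if the true lag is longer. Few events should be affected. The undefined status of an onset with unknown year is a gap in the plan rather than a demonstrated loss. The absent stop-date check can produce impossible dates and over-counting. It is worth correcting because safety is the study's only reported outcome and the correction is cheap.

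**What to change.** Anchor every partial start-date rule in SAP 6.2 to the first HZNP-ACT-303 dose:
- If the known date parts do not place onset before first dose, and the stop date is not before first dose, impute the first-dose date (or the first day of the known later month or year) and class the event as treatment-emergent.
- Treat an onset that cannot be determined as treatment-emergent unless the stop date is before first dose.
- Never impute a start after a known stop.

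The same anchoring replaces the unknown-month instruction, "If the year matches the year of enrollment date, then impute the month and day of the randomization date", which relies on a date that this open-label extension does not generate.

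The cost is SAP wording and a few lines of code, with a possible slight over-count of TEAEs. No data collection changes.

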8.6.3 Populations for Analysis

All analyses will be based on the Safety Population. The safety population will be all subjects who receive at least one dose of study drug on or after the Baseline/Day 1 Visit.

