5. ANALYSIS POPULATIONS

The following analysis populations are planned for this study:

• **Safety Population (SAFETY):** The Safety Population includes all subjects who receive at least one dose of open-label study drug after the Baseline Visit for HZNP-ACT-303. All analyses will be based on the Safety Population unless otherwise noted.

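### SAP 6.2 imputes some adverse-event start dates to a randomization date that open-label study 303 does not have, which can place onset before first dose

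*SAP*

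**What the plan says.** SAP 6.2 sets the convention for partial start dates. Month unknown: "If the year matches the year of enrollment date, then impute the month and day of the randomization date"; otherwise 01 January is assigned. Day unknown: "If the month and year match the month and year of the enrollment date, then impute the day of the first dose date"; otherwise day 01 is assigned. One rule therefore uses three anchors: enrollment for the matching test, randomization for one imputed value, and first dose for the other.

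SAP 9.1 brings adverse events under this rule: "Missing and partially missing AE start and/or stop dates will be imputed for the purpose of statistical analysis", by reference to Section 6.2. SAP 6.3 then decides treatment-emergent status by whether the event "occurs on or after the date of the first dose of study drug through the duration of the clinical study". Protocol 8.5.2.1.2 makes clear that the dose in question is the first one in study 303.

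On design, SAP 3 and Protocol 8.4.8 and 8.4.9 describe an open-label extension in which every subject receives ACTIMMUNE. Protocol 6.2 identifies HZNP-ACT-301, two studies earlier, as the randomized trial.

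After its rules for missing severity and relationship, SAP 6.2 closes with "No other missing data will be imputed unless otherwise specified". Neither SAP 6.2 nor SAP 6.3 gives a default treatment-emergent status for an event whose onset cannot be determined.

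**The concern.** The value to be imputed does not exist in this study, so whoever programs the rule must choose a substitute. The choice matters because treatment-emergent status turns on a single date comparison, and a difference of one day can reverse it.

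Long-term safety is the study's only objective, and SAP 8 and 10 drop the efficacy analyses. The treatment-emergent tables are therefore the main output. An event wrongly dated before first dose would leave those tables. That runs against the cautious direction SAP 6.2 takes elsewhere, where missing severity becomes severe and missing relationship becomes related.

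**Working it through.** The plan gives no figure to reproduce. The check is a date comparison under the two plausible substitutes for the missing anchor.

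**Inputs**

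- Enrollment date E, taken as Day 1, when consent and eligibility review take place (Protocol 8.5.4.1).
- Drug is distributed on Day 1 for home use on the three-times-weekly schedule (Protocol 8.5.4.1).
- Example schedules: Monday/Wednesday/Friday and Tuesday/Thursday/Saturday (Protocol 8.4.7.3).
- Assumptions: visits fall on Monday to Friday, the first dose is taken on the first available schedule day, a dose on the visit day is allowed, and all combinations have equal weight.

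**Formula**

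First dose date F = E + lag. An event is treatment-emergent if imputed onset ≥ F.

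- Anchor read as enrollment: onset = E, so the event is treatment-emergent only if lag = 0.
- Anchor read as first dose: onset = F, so the event is always treatment-emergent.

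**Lag in days from visit to first dose**

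| Visit day | Mon/Wed/Fri | Tue/Thu/Sat |
|---|---|---|
| Mon | 0 | 1 |
| Tue | 1 | 0 |
| Wed | 0 | 1 |
| Thu | 1 | 0 |
| Fri | 0 | 1 |

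Lag 0: 3 + 2 = 5 combinations. Lag 1: 2 + 3 = 5 combinations. Under the enrollment reading, 5 of 10 combinations (50%) date an affected event one day before first dose. Under the first-dose reading none do. If every subject doses on Day 1, the enrollment reading gives none either.

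**Example**

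A subject enrolls on Friday 15 July 2016 and follows the Tuesday/Thursday/Saturday schedule, so the first dose is on Saturday 16 July. An event is recorded with start year 2016 and month unknown. The enrollment anchor gives onset 15 July, before 16 July, so it is not treatment-emergent. The first-dose anchor gives 16 July, so it is. The true onset could have been any time up to December.

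**Matching test**

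Both branches test the year or month of enrollment, not of first dose. With a lag of at most one day this makes no difference to status: if first dose falls in the next month it falls on day 01, which is the date the fallback assigns. Aligning the test with first dose is for consistency and guards against longer lags.

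**The case against.** The strongest reply is that this is a one-word template slip. The same sentence tests the enrollment date, so a programmer would substitute it, and the resulting onset would be at most a day out on the schedules above and exact for anyone who doses on Day 1. The slip is likely, but the substitution does not cure it, because a one-day error is enough to change treatment-emergent status.

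The second reply is that hardly any events will qualify, and this stands. The year must be known, the month unknown, and the year that of enrollment. Adverse events are asked about roughly every three months (Protocol 8.1 and 8.5.4.2), start and stop dates belong in the source documents (Protocol 9), and omissions are checked for (Protocol 12). No hypothesis is tested, and SAP 9.1 lists every event.

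Four stronger inferences are tempting but are not supported:

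- *Affected events simply have no onset.* That is the literal result, but the sentence itself suggests a substitute, so it should not be presented as what will happen.
- *First dose never falls on Day 1, so every affected event is lost.* SAP 5 defines the population by "at least one dose of open-label study drug after the Baseline Visit for HZNP-ACT-303", but a home dose later on the visit day satisfies that, and neither document rules it out.
- *The term means randomization in HZNP-ACT-301.* The SAP does not point to that date, and the documents do not give the interval from 301 to 302, so no dependable figure can be attached to this reading.
- *Medications need their own rule.* The convention does cover medication start dates, but a separate rule would depend on eCRF fields that cannot be seen here.

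**Conclusion.** The rule is wrong as written, and the fault is minor. SAP 6.2 anchors one class of adverse-event start dates to a date that study 303 does not have. The most natural substitute, enrollment, still places an affected event before first dose whenever the first home dose follows Day 1.

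On the stated assumptions that is 5 of 10 visit-day and schedule combinations, by one day. This is a share of combinations, not of events or subjects, and it falls to zero if everyone doses on Day 1. The number of affected events cannot be derived from the documents and is probably very small. The wording error is certain; its effect on the tables is not.

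**What to change.** In the month-unknown branch of SAP 6.2, replace the randomization date with the date of first dose in HZNP-ACT-303, as the adjacent day-unknown branch already does in substance. For adverse events, use that same date for the matching test in both branches: the year of first dose when the month is unknown, and the month and year of first dose when only the day is unknown. Keep 01 January and day 01 as the fallbacks.

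Make two exceptions in which onset is not moved to first dose: a known stop date earlier than first dose, and an event recorded as ongoing from HZNP-ACT-302, which Protocol 8.5.2.1.2 treats as a baseline sign or symptom.

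The cost is a few lines of SAP text and a small programming change before database lock. The downside is that an undocumented pre-dose event with no stop date may be counted as treatment-emergent. The new anchor would also date a medication with the same kind of partial start date to first dose, so it would not count as prior under SAP 6.3; this should be noted when the change is made.
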